In low doses, naltrexone acts as a neuroprotective glial modulator by inhibiting activation of microglia, which are central nervous system immune cells, activated by various stressors. Upon activation, they produce inflammatory and excitatory molecules, resulting in a pro-inflammatory cascade, leading to neurotoxicity. Naltrexone specifically binds as an antagonist to Toll-like receptor 4 (TRL4). TLR4 has downstream cellular signaling leading to pro-inflammatory cytokines including interlukin-1, tumor necrosis factor-alpha, interferon- beta, excitatory amino

acids, substance P, and nitiric oxide, resulting in neuroinflammation, (23, 24, 25, 29, 31). TLR4 is expressed in the lower urinary tract of both humans and mice (36). LDN also plays a role in modulating the neuroimmune axis by its action on maturation of dendritic cells and in mitochondrial apoptosis (23).

LDN also upregulates opioid signaling by intermittent blockade of opioid receptors for 4-6 hours, creating a rebound effect, increasing endogenous opioids (22) and upregulates opioid signaling, by increasing the production of opioid receptors. (25) One of the endogenous opioids increased, beta-endorphins, is known to have anti-inflammatory properties (23, 24). The increased production of endogenous opioids may also inhibit the proliferation of B and T lymphocytes, and modulate the immune system (23, 25). Furthermore, upregulated endorphins may produce neuropsychological benefits (29).

Some adverse effects have been reported with the use of LDN. Vivid dreams, nightmares and insomnia are possible side effects, which can be mitigated by changing drug administration from bedtime to morning (23), and do improve with longer duration of taking LDN (34). There is also a reduction in pain relief from narcotics for at least six to 24 hours after taking low-dose naltrexone. In addition, low-dose naltrexone should not be used in patients who are currently receiving opioid analgesics. Naltrexone is designed to suppress cravings for opioid and alcohol use. Individuals with moderate to severe alcohol use disorder who take naltrexone may experience withdrawal symptoms if they stop drinking than can be potentially fatal due to the development of seizures. Individuals who use opioid pain medication and take naltrexone will not have the same pain relief, and may take more medication to overcome this, resulting in a potentially fatal overdose.

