Patients taking thyroid replacement may require a lower amount of thyroid medication and should have thyroid function tests performed regularly. Elevation of liver enzymes is a potential risk with naltrexone treatment, but is not felt to be common with low-dose therapy. Other potential side effects may include but are not limited to gastrointestinal disturbances, such as stomach cramps and diarrhea (24, 26, 35), agitation, anxiety, flu-like symptoms, and headaches. One case report reported increased yawning, dry mouth, and thirst (35). The effect of naltrexone on the menstrual system has had mixed results, with some studies reporting no differences (51, 52), while one study noted an increase in pulsatile luteinizing hormone and prolactin secretion (53). No studies with low-dose naltrexone have explored changes in the menstrual cycle.

Low-dose naltrexone should be compounded with short-acting fillers, and calcium carbonate should be avoided. LDN should be stopped at a minimum of 24 hours prior to the time narcotics may be needed for pain relief for a scheduled surgical procedure (24, 26). Absolute contraindications include pregnancy and opioid dependence. (23)

Summaries of studies conducted to date

There have been no studies investigating the efficacy of using LDN in the treatment of IC/PBS to date. Studies have shown benefit in helping to relieve pain in patients with fibromyalgia(38, 42), complex regional pain syndrome (40) and chronic low-back pain (38). These conditions are commonly associated with IC/PBS. Studies with LDN have also demonstrated improvement in disease activity in autoimmune conditions like inflammatory bowel disease and multiple sclerosis(22, 24, 25, 29, 30, 31, 32, 33). There is also evidence that LDN may enhance emotional

well-being (25, 34), life-satisfaction (34), and may be beneficial in some dermatologic conditions (29, 41).

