Patients diagnosed with IC/PBS by one of the urogynecology providers at the Center for Pelvic Health in the NorhShore University HealthSystem by diagnostic criteria for IC/PBS by AUA guidelines will be eligible to participate. A patient must then meet all applicable inclusion and exclusion criteria.

Inclusion criteria

- 1. Patients aged eighteen and older
- 2. Meet criteria for IC/PBS as defined by the American Urology Association as "an unpleasant sensation (pain, pressure, discomfort) perceived to be related to the urinary bladder, associated with lower urinary tract symptoms or more than six weeks duration, in the absence of infection or other identifiable causes" (8)

- 3. Newly diagnosed and treatment naïve for IC/PBS or previously diagnosed with IC/PBS, but who have no received treatment in the past four weeks. Patient who use anti-inflammatory medication on an as needed basis in the four weeks prior to the study will be included.
- 4. Have had a cystoscopy in the last 6 months prior to study entry to rule out confounding conditions
- 5. English speaking
- 6. Working telephone number
- 7. Able to attend research visits

Exclusion criteria:

- 1. Patients under the age of 18
- 2. Patients with known liver disease, including total bilirubin >1.2, AST> 32, ALT> 54 within the last six months or with enrollment screening testing
- 3. Patients with known kidney disease
- 4. Patients who have thyroid disease and who are taking thyroid replacement medications
- 5. Patients with known neurologic disease affecting bladder function
- 6. Patients with known bladder or urethral cancer
- 7. Patients with bladder, urethral, or ureteral calculi
- 8. Patients who have had a positive urine culture or a clinical UTI in the past 6 weeks
- 9. Patients who are currently pregnant or breast feeding (15)
- 10. Patients who are actively using opioid analgesics
- 11. Patients with moderate-severe alcohol use disorder
- 12. Patients who are actively using sleep aids
- 13. Patients who are regularly using anti-inflammatory medications, such as daily Celebrex for arthritis. Those who use an anti-inflammatory medication on an as needed basis may use the medication prior to enrollment in the study.
- 14. Patients who have had a known adverse reaction to naltrexone
- 15. Patients who are acutely ill
- 16. Patients who are diagnosed with a significant psychological comorbidity that would interfere with study participation (32)

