- 17. Patients who have had a bladder instillation or had oral medical treatment for IC/PBS in the past four weeks.
- 18. Patients diagnosed with other chronic pelvic pain syndromes, such as endometriosis
- 19. Patients who are unable to swallow pills/capsules
- 20. Patients who have had previous treatment with low-dose naltrexone
- 21. Patients who have previously scheduled surgeries or procedure during the study time period that would require analgesia.
- 22. Patients who are sexually active and of childbearing potential who are unwilling to use an established and reliable form of contraception for the duration of the study.
- 23. Patients who are unwilling to have a serum blood test to assess serum transaminases and serum bilirubin.

Withdrawal criteria:

Patients can self-withdrawal at any time from this study, and they will be informed that doing so will have no impact on their medical care within the practice. Patients who become pregnant, experience serious adverse effects, or are deemed unable to continue the study for by study personnel will be withdrawn by study personnel. In the

event of withdrawal from the study, the participant will be asked to return any unused study medication.

Human Subject Protection Rationale for Subject Selection

Patients meeting criteria by the American Urology Association definition of IC/PBS are the ideal study population to investigate a novel therapy for IC/PBS.

Evaluation of benefits, risks and discomforts

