Drug preparation: The LDN study medication and placebo will be compounded and prepared by Keefer's pharmacy.

Drug dispensing and accountability: The medication will be dispensed by the Skokie NorthShore pharmacy to the research personnel to provide to the participant. Participants will return their pill vial, including any unused medication at the time of their six-week follow up visit. Any residual medication will be documented, and the medication returned to the pharmacy for disposal by onsite destruction.

Drug administration: the patients will take their appropriate randomized medication for a total of six weeks. The first two weeks, patients will take one capsule at night, and for the last four weeks, they will take two capsules at night.

Contraindications/concomitant medications: Absolute contraindications to taking LDN include pregnancy, moderate-severe alcohol use disorder, and opioid dependence. In the case reports and small randomized trials, LDN does not appear to interfere with other medications patients were taking at the time of the study.

Breaking the blind: In the event of an adverse event, a phone call can be made to the NorthShore Skokie inpatient pharmacy to determine if they are taking the study medication or placebo. If this should occur, the phone call should be followed up with written documentation in the form of an email with notification of the break in the blind.

Drug destruction: Study participants will be requested to return the pill vials to clinic. Any residual medication will be documented, and the medication returned to the pharmacy for disposal by onsite destruction.

Medication compliance assessment: Study participants will be requested to return the pill vials to clinic. Any residual medication will be documented, and the medication returned to the

pharmacy for disposal by onsite destruction. Participants will also be asked to keep a log of when they take their medication.

Safety Assessment

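### Exclusion 10 bars active opioid analgesic use, which is narrower than the opioid dependence that the protocol calls an absolute contraindication

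*Combined protocol and SAP*

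**What the plan says.** The combined protocol and SAP makes two kinds of statement about opioids and LDN.

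- **Contraindication.** Study drug and comparator, under contraindications and concomitant medications: "Absolute contraindications to taking LDN include pregnancy, moderate-severe alcohol use disorder, and opioid dependence". Background and Significance says the same of two of these conditions: "Absolute contraindications include pregnancy and opioid dependence". The later section on potential benefits, risks and adverse effects again lists opioid dependence as a contraindication.
- **Warning about current use.** Background and Significance also says that "low-dose naltrexone should not be used in patients who are currently receiving opioid analgesics".

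The only eligibility criterion that names opioids is exclusion 10: "Patients who are actively using opioid analgesics". It gives no interval for what counts as active.

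Screening/eligibility determination makes the inclusion and exclusion criteria the condition for taking part. The consent section says that potential participants are asked about those criteria.

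**The concern.** Dependence and active analgesic use overlap but are not the same. Exclusion 10 follows the warning about current use and leaves the wider contraindication out of the list. Someone screening from the numbered list, in person or by telephone, could find no criterion that bars a patient whom the study drug section says must not take LDN.

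What is at stake is participant safety, and it differs by group. For dependent patients on maintenance or non-prescribed opioids, the case rests on the protocol's own statement that dependence is an absolute contraindication. For those who recently stopped, there is also the warning that people taking opioid pain medication with naltrexone may raise their dose to overcome the block and suffer a fatal overdose. That warning applies to them only if they resume such medication.

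**Working it through.** No arithmetic beyond counting applies, and the plan gives no figure to reproduce. The check sets the contraindications beside the eligibility list.

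**Step 1. Match each absolute contraindication in the study drug section to the exclusion list.**

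| Contraindication | Exclusion item | Match |
|---|---|---|
| Pregnancy | 9: "Patients who are currently pregnant or breast feeding" | Direct |
| Moderate to severe alcohol use disorder | 11: "Patients with moderate-severe alcohol use disorder" | Direct |
| Opioid dependence | 10: "Patients who are actively using opioid analgesics" | Partial |

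So 2 of 3 are carried over directly, and 3 − 2 = 1 is not. Opioids are named in 1 of 23 exclusion items. Opioid dependence is named in 0 of 23 exclusion items and 0 of 7 inclusion items.

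**Step 2. Ask which dependent patients the list already stops.**

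- Those now taking opioid analgesics: item 10.
- Those who took an oral opioid as treatment for IC/PBS within four weeks: item 17 ("Patients who have had a bladder instillation or had oral medical treatment for IC/PBS in the past four weeks") and, for patients with an existing diagnosis, inclusion 3 ("previously diagnosed with IC/PBS, but who have no received treatment in the past four weeks").
- Some others, at staff discretion: item 16, on psychological comorbidity. It needs a diagnosis judged to interfere with participation, and it does not mention substance use.

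**Step 3. Ask who remains without an express exclusion.**

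- Dependent patients on maintenance or non-prescribed opioids, where that use is not regarded as analgesic.
- Dependent patients who have just stopped opioids taken for something other than IC/PBS. Item 10 sets no interval, whereas items 2, 8 and 17 state theirs (six months, six weeks and four weeks).

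**Step 4. Look for controls before the first dose.** Baseline Evaluation collects pain medication use in the last month, medical history and current medications. Study procedures places the intake forms third, randomization fourth and drug distribution seventh, so staff see this information before they dispense. Participants must also wait for normal liver results before starting. These steps may reveal dependence, but no listed criterion then makes the patient ineligible, and a question about pain medication need not bring out maintenance or non-prescribed use. The record entry that alerts other providers and the two-week call come after enrolment.

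**The case against.** The strongest reply is that the protocol already deals with this. Opioid dependence is named as a contraindication in three places, one of them the operative study drug text. Passing the list is necessary for entry, but nothing obliges staff to enrol someone who must not take the drug. This stands, and it keeps the point small. It does not remove the point: the protocol did not leave pregnancy or alcohol use disorder to the drug section alone.

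Second, item 10 can be read by drug class. It does not require that the opioid be prescribed or taken for pain, so it may cover non-prescribed painkillers and arguably maintenance with an opioid that is also an analgesic. That is a fair reading and it shrinks the first group. The wording does not settle it, and staff could reasonably read it either way.

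Third, the telephone script, demographic questionnaire and consent form are listed as appendices but were not available. They may ask about opioids directly. This stands, so the fix is conditional on it.

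A reader might go further and infer that any opioid use within four weeks should be barred, to match item 17 and inclusion 3. The documents do not support that. Those windows are a washout for IC/PBS treatment, and such a ban would exclude a non-dependent patient after one past dose. The opioid intervals in the Background (6 to 24 hours of reduced narcotic relief after LDN, and stopping LDN at least 24 hours before planned narcotics) concern opioids taken after LDN. No opioid-free period before starting LDN is given.

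**Conclusion.** The point holds as a minor mismatch between sections: exclusion 10 is narrower than the protocol's own absolute contraindication, and the enrolment list does not expressly exclude all opioid dependence.

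Two stronger inferences should be resisted. The protocol does not permit dosing of dependent patients, because the study drug text rules it out; the fault is that the rule sits outside the eligibility list. Nor can a frequency be put on the gap. The Background mentions opioid use during the study as one of the reasons that five of forty patients left a multiple sclerosis pilot, but that is neither dependence at entry nor this population.

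The conclusion assumes that dependence is a wider category than active analgesic use, and that screeners work from the numbered list, as the screening section describes. That few patients are affected is a judgement. The sample size and the analysis are unaffected.

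**What to change.** Reword exclusion 10 to: *Patients with opioid dependence, or currently using any opioid (analgesic, maintenance or non-prescribed).* Ask about both directly at screening, and add the question to the telephone script and demographic questionnaire only if they lack it.

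Do not add a four-week ban on any opioid use. If a minimum opioid-free interval before the first dose is wanted, the investigator and pharmacy should set it.

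The cost is one wording change, at most one screening question, and probably no more than a few extra screen failures; the documents give no figure from which to estimate that number.

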Premenopausal study participants will be advised to keep a menstrual cycle chart to monitor any deviation from their regular cycle, which will be provided to them. They will be informed that in the event of any menstrual irregularity, they should inform study personnel, and they should be thoroughly evaluated in our office, including a pregnancy test.

In addition, study participants will be advised not to breastfeed while participating in the study. The use of low-dose naltrexone in breastfeeding has not been studied.

The study consent form states the following, and will be reviewed with all potential study participants:

"You should not become pregnant while on this study. It is not known whether the study drugs will affect an unborn baby, a pregnant person, or impact sperm. You should use effective birth control methods if you become pregnant and you wish to be in this study. If you become pregnant during this study, you should notify the study doctor right away. If you become pregnant you will have to stop participation in the study. Birth control may not stop pregnancy. Only totally stopping sexual intercourse can guarantee that pregnancy will not happen. If you think your birth control has failed, you should not rely on home pregnancy tests. Instead, you need to call your study doctor right away to arrange for medical pregnancy tests.

You should discontinue all study medications should you become pregnant.

Additionally, you should not be breastfeeding an infant/toddler while in this study"

COVID-19 Risk

COVID-19 poses a real risk to the safety of study participants and research personnel. This study protocol was written prior to the start of the pandemic. As such, a step-by-step start up plan was created in March 2021 to minimize the risk of exposure to the virus by study participants and research personnel. Please see the attached document for specifics of the protocol.

Consent and assent process and documents

To qualify, patients must first be diagnosed with IC/PBS by one of the urogynecology providers at the Center for Pelvic Health in the NorhShore University HealthSystem. As this patient population is difficult to identify based on chief complaint, potential study participants will be recruited after diagnosis of IC/PBS.

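### The only birth-control instruction in the quoted consent text applies to participants who become pregnant, so it reaches nobody who may stay in the trial; correct it and check the consent form

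*Combined protocol and SAP*

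**What the plan says.** The Reproductive risk section introduces the consent excerpt with "The study consent form states the following, and will be reviewed with all potential study participants". The third sentence of that excerpt is "You should use effective birth control methods if you become pregnant and you wish to be in this study".

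The rest of the protocol treats pregnancy and contraception as follows.

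- Exclusion criterion 9 bars "Patients who are currently pregnant or breast feeding".
- Exclusion criterion 22 bars "Patients who are sexually active and of childbearing potential who are unwilling to use an established and reliable form of contraception", with the requirement running through the whole study.
- The withdrawal criteria have study personnel remove "Patients who become pregnant, experience serious adverse effects, or are deemed unable to continue the study".
- The body of Reproductive risk requires participants who are sexually active and of childbearing potential to have a urine pregnancy test at the start and to use an established contraceptive method while in the study.
- Two sentences after the one at issue, the excerpt itself states "If you become pregnant you will have to stop participation in the study".

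**The concern.** The sentence ties birth control to the wrong event. Contraception is needed before pregnancy, by people who could conceive. As written, the duty falls on someone who is already pregnant and wants to be in the study, and the protocol does not allow that person to take part.

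What is at stake is a safety instruction addressed to participants. The protocol calls the reproductive risks of low-dose naltrexone unknown. It lists pregnancy as an absolute contraindication, both in the background and under contraindications/concomitant medications. If the consent form carries the same wording, its one direct instruction on birth control does not state the rule that participants are held to. Patients are encouraged to discuss the form with family and outside physicians, and they may receive it by mail. Such readers would have the form's wording in front of them and not exclusion 22.

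**Working it through.** No calculation applies, and the plan gives no figure to reproduce. The check compares texts and makes two simple counts.

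**Step 1: who can meet the condition.** The sentence needs a person who becomes pregnant and wishes to be in the study.

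- Before entry: a pregnant patient is excluded (criterion 9).
- After entry: a participant who becomes pregnant is withdrawn (withdrawal criteria), is told to stop the medication and notify staff (Reproductive risk), and is told in the same excerpt that she must stop.

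A participant could become pregnant, but she could not then remain. The condition therefore describes nobody whose participation is permitted.

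**Step 2: who should be covered.** The three statements of the contraception rule compare as follows.

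| Place | Who must use contraception | For how long |
|---|---|---|
| Exclusion criterion 22 | Sexually active, of childbearing potential | Whole study |
| Reproductive risk, body text | Sexually active, of childbearing potential | Whole study |
| Reproductive risk, consent excerpt | Those who become pregnant and wish to take part | Not stated |

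The first two agree; the third differs in both population and duration. So 2 of 3 are correct, and the exception is the one written for participants.

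**Step 3: whether another sentence in the excerpt fills the gap.** The excerpt has 11 sentences. The nearest candidates are these.

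- "You should not become pregnant while on this study" sets the aim but does not say that birth control is required, or of whom.
- "If you think your birth control has failed, you should not rely on home pregnancy tests" presupposes that birth control is in use but does not require it.
- Two further sentences say that birth control can fail and that only abstinence is certain. Neither tells anyone to use a method.

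That leaves 1 of 11 sentences instructing the use of birth control, and it is the faulty one.

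**Step 4: how many people are affected.** The planned sample is 44 (Sample Size). The protocol does not say how many of them would be sexually active and of childbearing potential, so the number to whom the correct rule applies cannot be narrowed from the documents.

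**The case against.** The strongest reply is that this is an evident drafting slip with little practical consequence. The probable intent was a phrase such as 'could become pregnant', and most readers would supply it. The sentence names the wrong group but tells nobody to go without contraception, and the surrounding sentences point the right way. Staff also apply the correct rule independently of the form:

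- screening on the exclusion criteria comes before the consent form is given out;
- consent is obtained in clinic by research personnel, even when the form was mailed first;
- the baseline questionnaire asks premenopausal participants what contraception they use;
- premenopausal participants have a urine pregnancy test at enrolment and are advised to keep a menstrual chart, with evaluation and a further pregnancy test if there is any irregularity.

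Finally, the consent form (Appendices, item 1) is not in the supplied text, so the error may exist only in the protocol's copy.

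Most of this stands, and it sets the weight of the point. These safeguards make an actual failure of contraception because of this sentence unlikely, and mailing the form does not bypass the clinic review. The intended wording is an inference, however, because the documents do not give it. Nor do the safeguards make the sentence correct. The protocol presents it as what the consent form says, and participants should be able to rely on that text.

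**Conclusion.** The point holds: the sentence is wrong as written. It assigns the duty to use birth control to people who may not be in the trial, and it omits those to whom exclusion 22 and Reproductive risk assign it. It is a minor wording error in participant-facing safety text, with no effect on sample size, error rates or analysis.

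The conclusion rests on the protocol text as supplied. A word lost in converting the PDF cannot be fully excluded, although the sentence is complete and shows no gap. Whether the consent form in use has the same error is open, and any need to contact participants depends on that.

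**What to change.** Replace the sentence with: *If you are sexually active and could become pregnant, you must use an effective birth control method for the duration of the study.* The population and duration come from exclusion 22 and Reproductive risk, so no new requirement is added.

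Then check the consent form. If it has the same error, submit a corrected form to the IRB and inform or re-consent current participants as the IRB directs. If it does not, correct only the protocol copy.

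The cost is one sentence in the protocol and one check of the form. An IRB submission and contact with enrolled participants arise only if the form is also wrong.
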